1.2 SCHEMA

Week 0

Medical Screening and Enrollment

- Obtain informed consent
- Screen potential participants by inclusion and exclusion criteria with online, phone, and medical screening via gynecological exam and mammogram
- Obtain history, document

Week 8

Lab Session- Baseline Assessments

- Administer STAI and SHAPS questionnaires
- Administer Dot Probe and EEfRT behavioral tasks
- Administer Trier Social Stress Test (TSST) and collect serum to measure cortisol at the end of baseline rest and at minutes 20, 30, and 45 of recovery post-TSST
- Urine HCG test to confirm subject is not pregnant prior to randomization

Randomization

- Active Intervention Group (0.10mg transdermal estradiol (E2))
- Placebo (matching inactive patch)
- Administer initial dose of study drug intervention

Week 16

Lab Session- Study Intervention, Side Effect & Compliance Checks

- Administer STAI and SHAPS questionnaires
- Administer Dot Probe and EEfRT behavioral tasks
- Administer Trier Social Stress Test (TSST) and collect serum to measure cortisol at the end of baseline rest and at minutes 20, 30, and 45 of recovery post-TSST
- Administer oral micronized progesterone (200mg daily)/matching placebo capsules for subjects to take for twelve days starting on Week 17 for the same treatment arms as E2/placebo randomization

Week 20

Lab Session- Study Intervention, Side Effect & Compliance Checks

- Administer STAI and SHAPS questionnaires
- Administer Dot Probe and EEfRT behavioral tasks
- Administer Trier Social Stress Test (TSST) and collect serum to measure cortisol at the end of baseline rest and at minutes 20, 30, and 45 of recovery post-TSST
- Continued administration of transdermal E2/placebo patch

Week 24

Final Lab Session- Study Intervention, Side Effect & Compliance Checks

- Administer STAI and SHAPS questionnaires
- Administer Dot Probe and EEfRT behavioral tasks
- Administer Trier Social Stress Test (TSST) and collect serum to measure cortisol at the end of baseline rest and at minutes 20, 30, and 45 of recovery post-TSST
- Administer oral micronized progesterone (200mg daily)/matching placebo capsules for subjects to take for twelve days starting on Week 25 for the same treatment arms as E2/placebo randomization
- Discontinue use of transdermal E2/placebo patch

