1.3 SCHEDULE OF ACTIVITIES (SOA)

Procedures	Medical Screening and Enrollment Week 0	Lab Session- Baseline Assessments & Randomization Week 8	Lab Session- Study Intervention, Side Effects, and Compliance Checks Week 16	Lab Session- Study Intervention, Side Effects, and Compliance Checks Week 20	Final Lab Session- Study Intervention, Side Effects, and Compliance Checks Week 24
Informed consent	X				
Demographics	X				
Medical history	X				
Physical and gynecological exam (including height and weight)	X				
Screening mammogram	X				
Pregnancy test ^a		X			
Randomization		X			
Administer transdermal estradiol/placebo		X	X	X	
Administer micronized progesterone/placebo			X		X
Discontinue transdermal estradiol/placebo					X
Administer STAI and SHAPS questionnaires		X	X	X	X
Administer Dot Probe and EEfRT behavioral tasks		X	X	X	X
Administer Trier Social Stress Test (TSST) and collect serum to measure cortisol ^b		X	X	X	X
Adverse event review and evaluation		X	X	X	X

a: urine pregnancy test (women of childbearing potential)
 b: serum collected at the end of baseline rest and at minutes 20, 30, and 45 of recovery post-TSST

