A total of 250 women in the early or late MT who are eligible for the hormonal probe will be recruited to reflect the full continuum of anxiety and anhedonia symptoms based on self-report to the State-Trait Anxiety Inventory and the Snaith-Hamilton Pleasure Scale, respectively. At baseline week 8, HPA axis (plasma cortisol) response to the Trier Social Stress Test and behavioral measures of threat responsivity (via Dot-Probe task) and approach motivation (Effort Expenditure for Rewards Task 'EEfRT') will be determined. Using transdermal E2 as a pharmacological probe to stabilize variability of E2 in premenopausal ranges, women will then be randomized to transdermal E2 (0.10 mg) or placebo for 16 weeks. This is not a clinical efficacy trial. We will use an RCT design with a hormonal manipulation to investigate the pathophysiologic role of E2 variability (or E2 levels) in HPA axis dysregulation and, in turn, threat responsivity and approach motivation. HPA axis reactivity to stress and behavioral responses to the Dot-Probe and EEfRT tasks, as well as self-report symptoms on the STAI and SHAPS measures will be assessed at weeks 8, 12, and 16 during the 16-week probe.

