The Trier Social Stress Test (TSST) involves social evaluation of speech and serial subtraction stress and induces large HPA axis responses 122-125. Baseline Rest (30 mins): The subject will rest for 30 minutes. Instructions: (5 min) Subjects are introduced to a 2-person committee. The subject will assume the role of a job applicant who is invited for a personnel interview with the committee. Anticipation: The subject prepares for 10 min. Speech: The committee asks the subject to deliver her talk for 5 mins. The committee responds with prepared questions to ensure that the talk lasts for 5 mins. Serial Subtraction: The subject is given a number to start from and asked to subtract a number from that original number as fast and as accurately as possible for 5 mins. For each mistake, the subject restarts at the original number. Stress Recovery: The subject rests alone for 45 mins. The characteristics of the TSST that elicit large HPA axis response include: 1) lack of controllability; 2) creation of a context of forced failure; and 3) social evaluative threat²⁸. Thus, the TSST provides a physiologic unit of analysis for the construct of threat responsivity. To minimize habituation, we will use the second TSST at baseline week 8 as the comparison for all analyses (the first TSST will be used to eliminate the novelty effect). Modifications with each TSST will minimize habituation:¹²⁶ 1) a different speech topic, such as modifying the job; describing one's positive and negative personality attributes and impact on likeability¹²⁶; 2) different numbers in the serial subtraction; 3) different, opposite sex committee members each time. With these modifications, some novelty is maintained even with repeat exposure, ensuring a significant HPA response.

Neuroendocrine Sampling during Stress Testing: Plasma cortisol will be taken at the end of baseline rest and again during Recovery at minutes 20, 30, and 45, wince HPA-axis reactivity is reliably seen 10-30 minutes after cessation of the TSST ^{22,26}.

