9 STATISTICAL CONSIDERATIONS

NOTE: There will not be a formal Statistical Analysis Plan (SAP) attached to this protocol. Rather, details on all analysis plans are to be found in this section under the specific subheadings. We will test whether there are any differences between related population means (time effect, within-subject) and whether mean levels change across time based on the treatment group the participants were randomized to (time x treatment effect, within and between-subject).

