9.4.3 ANALYSIS OF THE SECONDARY ENDPOINT(S)

All analyses of the secondary endpoints are independent of the primary endpoints.

For each secondary endpoint:

1. Changes in Cortisol stress response

The cortisol response will be presented as Area Under the Curve (AUC) with respect to ground and calculated using the trapezoid formula described by Pruessner¹⁷⁷. At weeks 8, 16, 20, and 24, cortisol was assessed around a standardized psychosocial stress test – the Trier Social Stress Test. Before the stress test, a baseline, pre-stress serum sample was taken. After the end of the stress test, reactivity serum samples were taken at 10-, 20-, 30-, and 45-minutes post-stress. The distribution of the values at every single timepoint, at every week will be visually inspected and, in case of skewness, log-transformed before calculating the AUC. All AUC's will be treated as continuous, interval scaled measures and treated as repeated measure (assessed at weeks 8, 16, 20, and 24). Results of the statistical procedures will be presented as adjusted means (least squared means) with standard errors. Outliers at 2 SD's or more above or below the mean will be winsorized. In case of missing values for one or more single timepoints around the stress task, the AUC will not be calculated and as a consequence treated as missing data. The statistical procedures we will apply (proc mixed) are robust to randomly distributed missing data.

2.&3. Changes in the EEfRT and Dot Probe task

Continuous, interval scaled sum scores will be used for statistical models testing changes in the EEfRT and the Dot probe task. Both scores will be treated as repeated measures (assessed at weeks 8, 16, 20, and 24). Results of the statistical procedures will be presented as adjusted means (least squared means) with standard errors. Outliers at 2 SD's or more above or below the mean will be winsorized. Missing data will not be imputed, as the statistical procedures we will apply (proc mixed) are robust to randomly distributed missing data.

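### Section 8.2 takes the second TSST as the cortisol baseline, but the schedule has only one TSST up to and including week 8, so the novelty run-in has no visit

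*Combined protocol and SAP*

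**What the plan says.** - **Section 8.2 (TSST description).** To limit habituation, "we will use the second TSST at baseline week 8 as the comparison for all analyses"; of the earlier one it says "the first TSST will be used to eliminate the novelty effect". It also varies the speech topic, the subtraction numbers and the committee at each TSST.
- **Section 1.2 (schema).** Week 0 is consent, history and eligibility: "Screen potential participants by inclusion and exclusion criteria with online, phone, and medical screening via gynecological exam and mammogram". Week 8 has a single entry: "Administer Trier Social Stress Test (TSST) and collect serum to measure cortisol at the end of baseline rest and at minutes 20, 30, and 45". Weeks 16, 20 and 24 have one each.
- **Section 1.3 (Schedule of Activities).** The row "Administer Trier Social Stress Test (TSST) and collect serum to measure cortisol" is marked at weeks 8, 16, 20 and 24. It is blank at week 0, and there is no column between weeks 0 and 8.
- **Section 2.1 (rationale).** One baseline response is described: "At baseline week 8, HPA axis (plasma cortisol) response to the Trier Social Stress Test".
- **Section 9.4.3 (cortisol analysis).** "At weeks 8, 16, 20, and 24, cortisol was assessed around a standardized psychosocial stress test". No run-in TSST is mentioned.
- **Section 9 (opening) and section 9.1.** "We will test whether there are any differences between related population means (time effect, within-subject"; the same sentence goes on to the time-by-treatment effect. The alternative hypothesis for cortisol AUC is change from week 8 on active treatment and none on placebo.
- **Sections 4.3 and 6.1.2.** The placebo arm is said to control for habituation to repeat testing.

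**The concern.** The protocol itself treats novelty as a bias to be removed before baseline, and section 8.2 names the device for removing it. That device has no visit, no date, no sampling rule and no statement that its data are left out of the analysis. A site working from the schema or the Schedule of Activities would give each woman her first TSST at week 8. The second would then fall at week 16, eight weeks after randomisation.

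At stake is what a change from week 8 means for the cortisol AUC. If the first exposure gives a higher response, both arms would tend to fall afterwards with no drug effect. The plan tests a time effect and states its hypothesis as change within one arm and no change within the other, so a fall from lost novelty could be credited to estradiol or could appear on placebo and contradict the hypothesis. There is also a risk of inconsistency: if some women had an unscheduled run-in and others did not, first-exposure and second-exposure baselines would be mixed. Section 9 says there is no separate SAP, so no other document defines the baseline.

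**Working it through.** **1. Counting TSSTs.**

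| Source | Up to and including week 8 | Whole study |
|---|---|---|
| Section 8.2 | at least 2 | at least 2 + 3 = 5 |
| Sections 1.2 and 1.3 | 0 + 1 = 1 | 1 + 3 = 4 |
| Section 9.4.3 | 1 | 4 |

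Section 8.3.4 also names laboratory sessions only at weeks 8, 16, 20 and 24. The schema's week 0 entry breaks off in the available text, but the Schedule of Activities independently shows no TSST at week 0.

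Two TSSTs in the one week 8 session would not fit what is listed. By section 8.2's timings one TSST takes 30 + 5 + 10 + 5 + 5 + 45 = 100 minutes, and only one set of cortisol samples is scheduled.

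**2. Which comparison is affected.** Suppose loss of novelty lowers the later values by h in both arms and the drug does nothing.
- Within-arm change from week 8: −h in each arm, so the time effect is also −h.
- Between-arm difference in change: (−h) − (−h) = 0.

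**3. Illustrative size.** The documents give no novelty figure, so h is assumed. Inputs:
- n = 60 per arm (sections 4.2 and 6.3) and two-sided alpha .05 (section 9.2).
- Correlation r = .25, the bound in section 9.2, and r = .5 as an assumed alternative.
- One-sample t-test on the week 8 to 16 change, used here to represent the within-arm hypothesis. The plan itself specifies a mixed model.

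With the outcome SD set to 1, the SD of change is √(2(1 − r)): √1.5 = 1.225 at r = .25, and 1 at r = .5. Noncentrality is h√60 / SD of change, and the critical value is 2.001 on 59 df. If p is the chance that one arm is significant and the arms are independent, the chance that active is significant and placebo is not is p(1 − p).

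| r | h (SD) | Noncentrality | One arm significant, p | Active significant, placebo not, p(1 − p) |
|---|---|---|---|---|
| .25 | 0.2 | 1.265 | 24% | 18% |
| .25 | 0.3 | 1.897 | 46% | 25% |
| .25 | 0.5 | 3.162 | 88% | 11% |
| .5 | 0.2 | 1.549 | 33% | 22% |
| .5 | 0.3 | 2.324 | 63% | 23% |
| .5 | 0.5 | 3.873 | 97% | 3% |

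With no shift the pattern has probability .05 × .95 = 4.75%.

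**4. Sensitivity.** Comparing week 8 with the mean of the three later visits, the variance of change is 1 + (1 + 2r)/3 − 2r, which is 1.00 at r = .25 and 0.667 at r = .5. The single-arm figures become 33%, 63% and 97% at r = .25, and 46%, 80% and nearly 100% at r = .5.

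The plan states no figure of its own on this point, so there is none to reproduce.

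**The case against.** The strongest reply is that the schedule is not exhaustive. Section 7.2 refers to weekly visits before randomisation and to baseline visits in the plural, and none of these has a column in section 1.3. Section 8.2 is the section specific to the procedure and commits to a first TSST, so a missing schedule entry is at least as plausible as a missing procedure. This stands. A reader might infer that the cortisol baseline is certain to be a novelty-inflated first exposure. The documents support that only if the schedule is followed as written.

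The second reply is that the randomised comparison is protected. Week 8 precedes randomisation, the sentence on the time effect continues to time by treatment, section 9.2 sizes the trial on the within-between interaction, and placebo is there to control habituation. This also stands, provided that the shift is additive and common to both arms. It does not protect the time effect or the within-arm form of the hypothesis, both of which are pre-specified.

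Third, the single-arm percentages could be read as the false-positive rate for the cortisol hypothesis. They are not. The hypothesis also requires no change on placebo, and under that condition the 88% and 97% become about 11% and 3%. A large novelty effect would mostly make the hypothesis fail rather than falsely succeed.

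Finally, section 8.2 varies topic, numbers and committee at each TSST and expects some novelty to persist. That may shrink the shift, but the protocol offers these measures alongside the run-in, not in its place.

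**Conclusion.** The contradiction is established by counting: section 8.2 needs at least two TSSTs by the end of week 8, and the schema and schedule provide one. As written, the baseline rule cannot be carried out on the schedule.

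The consequence is conditional. If no run-in is given, the time effect and within-arm changes in cortisol AUC mix lost novelty with any drug effect. Under assumed shifts of 0.2 to 0.5 SD, the hypothesised pattern would appear with no drug effect in about 3% to 25% of trials, against under 5% with no shift. That range rests on 60 women per arm, correlations of .25 to .5, independent arms and a week 8 to 16 t-test; the true shift is not in the documents. The documents do not support a claim that the treatment-by-time contrast is biased.

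Severity is moderate: cortisol AUC is a secondary endpoint, and neither primary endpoint is a TSST measure.

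**What to change.** Reconcile sections 1.2, 1.3, 8.2 and 9.4.3 in one of two ways.

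1. If the first TSST is to be run, enter it in the schema and Schedule of Activities before the week 8 baseline TSST, for every woman, and state that it is excluded from analysis. The cost is a schedule amendment for a procedure that 8.2 already commits to.
2. If it is not to be run, delete the statement about a second TSST from 8.2 and state that week 8 is the first exposure. The cost is wording only.

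In either case, state in sections 9.1 and 9.4.3 that cortisol conclusions rest on the treatment-by-time (between-arm) contrast, not on the time effect or on within-arm change. The price is that within-arm cortisol claims are given up.

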8.3 ADVERSE EVENTS AND SERIOUS ADVERSE EVENTS

8.3.1 DEFINITION OF ADVERSE EVENTS (AE)

Adverse event means any untoward medical occurrence associated with the use of an intervention in humans, whether or not considered intervention-related (21 CFR 312.32 (a)).

8.3.2 DEFINITION OF SERIOUS ADVERSE EVENTS (SAE)

An adverse event (AE) or suspected adverse reaction is considered "serious" if, in the view of either the investigator or sponsor, it results in any of the following outcomes: death, a life-threatening adverse event, inpatient hospitalization or prolongation of existing hospitalization, a persistent or significant incapacity or substantial disruption of the ability to conduct normal life functions, or a congenital anomaly/birth defect. Important medical events that may not result in death, be life-threatening, or require hospitalization may be considered serious when, based upon appropriate medical judgment, they may jeopardize the participant and may require medical or surgical intervention to prevent one of the outcomes listed in this definition.

8.3.3 CLASSIFICATION OF AN ADVERSE EVENT

8.3.3.1 SEVERITY OF EVENT

The following guidelines will be used to describe severity of AEs.

- **Mild** – is defined as having no effect on activities of daily living such as transient light headedness or sweating with venipuncture; breast tenderness, mild skin irritation; or something of equal significance that requires no medical intervention and is of marginal clinical relevance.
- **Moderate** – would be associated with temporary (minutes to a few days) disruption in activities of daily living such as temporary loss of consciousness with venipuncture; a worsening of migraines or headache that require bed rest, an increase in anxiety or anhedonia symptoms consistent with clinically meaningful levels, emergent suicide intent without specific plan (severity level 4 on the C-SSRS), excess sleepiness or fatigue that resolves with additional rest, or something of equal significance.
- **Severe** – would cause serious disruption in daily activities of living and may or may not require hospitalization. Examples of such events would include a thromboembolic event, breast carcinoma, an increase in blood pressure consistent with Stage 2 hypertension, any cardiovascular event, any event that is permanently disabling, any event requiring hospitalization or is life threatening, severe mood impairment or emergent suicide ideation with specific plan (severity level 5 on the C-SSRS) or any suicidal behavior (actual attempt, interrupted attempt, aborted attempt, or preparation towards imminent suicide attempt), or something of equal significance. The development of endometrial hyperplasia with or without atypia would also be consistent with a severe AE.

8.3.3.2 RELATIONSHIP TO STUDY INTERVENTION

- **Definitely Related** – There is clear evidence to suggest a causal relationship, and other possible contributing factors can be ruled out. The clinical event, including an abnormal laboratory test result, occurs in a plausible time relationship to study intervention administration and cannot be explained by concurrent disease or other drugs or chemicals.
- **Probably Related** – There is evidence to suggest a causal relationship, and the influence of other factors is unlikely. The clinical event, including an abnormal laboratory test result, occurs within a reasonable time after administration of the study intervention, is unlikely to be attributed to concurrent disease or other drugs or chemicals, and follows a clinically reasonable response on withdrawal. Rechallenge information is not required to fulfill this definition.
- **Not Related** – The AE is completely independent of study intervention administration, and/or evidence exists that the event is definitely related to another etiology.
- **Unknown** – based on the temporal relationship and clinical judgment of medical monitor, the relationship between the AE and study intervention cannot be determined.

8.3.3.3 EXPECTEDNESS

The Investigator gynecologist, PI, and study clinical psychologist will be responsible for determining whether an adverse event (AE) is expected or unexpected. An AE will be considered unexpected if the

nature, severity, or frequency of the event is not consistent with the risk information previously described for the study intervention.

8.3.4 TIME PERIOD AND FREQUENCY FOR EVENT ASSESSMENT AND FOLLOW-UP

The study coordinator will monitor side effects and AEs related to the pharmacological E2 probe at all study visits (on a weekly basis initially and then monthly for two months) and report all side effects as well as any significant deterioration in anxiety or anhedonic symptoms (see below) directly to [name] following study visits. Side effects consistent with moderate or severe AEs or that are troublesome to the subject, or evidence of mood deterioration reported by telephone, will also be immediately reported to [name]. Based on the clinical skill required not only to assess but to act on emergent suicidality, a licensed clinical psychologist or psychiatry resident will conduct the suicide assessments at each laboratory session (weeks 8, 16, 20 and 24) or more frequently if indicated (e.g., every two weeks for those with a history of suicide intent). Investigator licensed clinical psychologist, [name], will oversee the fellows and residents in this responsibility.

Bleeding patterns and severity will be assessed at every study visit. Moreover, subjects will be instructed to contact us whenever they start a menstrual bleed. Staff will follow up to determine the amount and duration of bleeding. For any woman with profuse bleeding (defined as more than 3 tampons or pads for more than 5 days OR more than 1 tampon or pad per hour on any given day), [name] will be contacted, and she will decide whether to evaluate if clinically indicated. The timing of the bleeding with respect to the timing of the progesterone will contribute to that determination. Any unscheduled or prolonged bleeding (> 10 days) will be followed by an ultrasound or an endometrial biopsy or both. If ultrasound reveals the vaginal the stripe thickness to be more than 3 mm, then an endometrial biopsy will be performed. If the pathology report indicates hyperplasia, the subject will be withdrawn from the study, estrogen discontinued, and [name] will prescribe a stronger progestin. If the subject has hyperplasia, a follow-up biopsy would be performed at 3 months to make sure it is cured. The research study will pay for all biopsies required, including the follow-up biopsy.

[name] will ensure that [name] or [name] are consulted within 24-hours of any severe AE. Moderate AEs will prompt a follow-up evaluation of the subject within one week. If the condition has not resolved or has worsened, [name] or [name] will be contacted to determine the next course of action. Staff will be specifically trained to monitor the STAI-S and the SHAPS for > 50% increase in symptom severity from baseline and an increase in stratification (e.g., from a low symptom group to a medium group or from a medium group to a high symptom group). If the subject is already in a high anhedonia or anxiety strata, then any increase above 50% will be reviewed by [name]. Staff will be specifically trained to monitor the STAI-S and the SHAPS for > 50% increase from baseline levels in symptom severity. In the case of elevations in anxiety and anhedonia symptoms [name] will determine the next course of action, including more frequent assessment of mood if deemed to be clinically required. In the case of emergent suicide ideation with intent or any suicide-related behavior, the individual will be withdrawn from the study and the blind broken. If the participant appears to need immediate treatment, she will be escorted to the UNC emergency department. Otherwise, [name] will meet with the participant to evaluate her safety and administer the C-SSRS. He will then determine the appropriate next steps, including referral to the UNC Center for Women's Mood Disorders or a community provider for further evaluation and treatment. [name] will be the responsible physician

to determine the next course of action involving medical side effects (e.g., continue in protocol, exclude, and refer for treatment).

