8.2 SAFETY AND OTHER ASSESSMENTS

Safety Screening prior to randomization:

- **Physical examination:** height and weight will be measured to determine eligibility based on BMI. Gynecological exam by Investigator gynecologist will determine if subjects have any signs or history of endometrial disorder, abnormal uterine anatomy, or abnormal ovarian anatomy (confirmed by endometrial ultrasound and/or biopsy).
- **Vital signs** Three stethoscopic blood pressure readings will be measured at enrollment to rule out hypertension.
- **Radiographic assessments.** Subjects will be required to have normal results from a screening mammogram within 12 months prior to enrollment.

The Snaith-Hamilton Pleasure Scale (SHAPS): ¹⁰⁴ assesses anhedonia. SHAPS scores range from 14-56, with higher scores corresponding to higher levels of anhedonia. This scale has shown adequate overall psychometric properties in clinical and student samples ¹⁰⁵. The SHAPS has satisfactory test-retest validity in healthy participants (intraclass correlation coefficient = 0.70, p < 0.001 ¹⁰⁶).

The State-Trait Anxiety Inventory (STAI): the state measure of anxiety from the STAI consists of items such as "I am worried" or "I feel calm" and participants complete the items as to how they currently feel. A higher score indicates higher anxiety. While there are no standard clinical cut-offs for the STAI, past research indicates scores ≥ 40 are clinically significant. ^{107,108} The scale has good median alpha reliability (.92). ¹⁰⁹

Dot-probe (DP) task (15 min): will measure attentional bias to threat (threat responsivity)¹¹⁹. An angry and a neutral face of the same individual are presented vertically simultaneously (trials with neutral faces are controls). Immediately following the face pair, a probe letter replaces either the angry face (threat congruent trial) or the neutral face (threat incongruent trial). Participants indicate the probe letter via button press. The task consists of 144 trials (48 threat congruent, 48 threat incongruent, 48 neutral). Trials are separated by a variable length inter-stimulus interval (900 - 1300 ms). Bias scores are calculated by subtracting the reaction time on threat congruent from threat incongruent trials. Positive scores reflect a bias towards threat and negative scores reflect a bias away from threat. Attention bias calculations exclude trials with incorrect responses, trials with reaction times <150 ms or >2000 ms or >2.5 SD outside the mean.

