9.4.2 ANALYSIS OF THE PRIMARY EFFICACY ENDPOINT(S)

For each primary endpoint:

1. Change in the Anxiety score from State-Trait Anxiety Inventory

State anxiety will be assessed using the validated State-Trait Anxiety Inventory. The State-Trait Anxiety Inventory consists of 20 questions on a 4-point force-choice Like-type response scale (scores 0 - 3). The 20 questions are summed together for a final score. The score can range from 0 to 60 with higher scores representing higher levels of anxiety. Continuous, interval scaled sum scores will be calculated and treated as a repeated measure (assessed at weeks 8, 16, 20, and 24). Change in State-Trait anxiety inventory will be analyzed using two-way repeated-measures analysis for a time and treatment effect (proc mixed in SAS). Models will use an auto-regressive covariance structure to account for the repeated assessments in the same participants. Outliers at 2 SD's or more above or below the mean will be winsorized. Missing data will not be imputed, as the statistical procedures we will apply (proc mixed) are robust to randomly distributed missing data. Before applying proc mixed, we will check for the randomness of missing data. Results of the statistical procedures will be presented as adjusted means (least squared means) with standard errors.

2. Change in anhedonia score from Snaith-Hamilton Pleasure Scale

Anhedonia will be assessed using the validated Snaith-Hamilton Pleasure Scale (SHAPS). Scores range from 0-14, with higher scores corresponding to higher levels of anhedonia. The questionnaire will be applied at weeks 8, 16, 20 and 24. Continuous, interval scaled sum scores will be calculated and treated as a repeated measure (assessed at weeks 8, 16, 20, and 24). Change in the SHAPS will be analyzed using two-way repeated-measures analysis for treatment x week (proc mixed in SAS). Models will use an auto-regressive covariance structure to account for the repeated assessments of primary and secondary outcomes in the same participants. Outliers at 2 SD's or more above or below the mean will be winsorized. Missing data will not be imputed, as the statistical procedures we will apply (proc mixed) are robust to randomly distributed missing data. Before applying proc mixed, we will check for the

randomness of missing data. Results of the statistical procedures will be presented as adjusted means (least squared means) with standard errors.

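### Section 8.3.4: the >50% review rule for women already in a high symptom stratum cannot fire once baseline reaches about two-thirds of the scale maximum

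*Combined protocol and SAP*

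**What the plan says.** Section 8.3.4 has staff trained to look on the STAI-S and SHAPS for a "> 50% increase in symptom severity from baseline and an increase in stratification", such as a move from the low to the medium group. It then adds the provision for women at the top: "If the subject is already in a high anhedonia or anxiety strata, then any increase above 50% will be reviewed by" a named member of the study team. A further sentence repeats the >50% threshold for both scales with no stratum condition. The next begins "In the case of elevations in anxiety and anhedonia symptoms" and leaves the course of action to clinical judgment, with no number attached.

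The scale ranges are given elsewhere. For the STAI, section 9.4.2 states: "The score can range from 0 to 60 with higher scores representing higher levels of anxiety". For the SHAPS there are two ranges. Section 8.2 says "SHAPS scores range from 14-56, with higher scores corresponding to higher levels of anhedonia" and section 9.4.2 says "Scores range from 0-14, with higher scores corresponding to higher levels of anhedonia". Section 8.2 also notes for the STAI that "past research indicates scores ≥ 40 are clinically significant". The cut-points of the low, medium and high strata are not stated.

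**The concern.** The authors saw that a woman in the top stratum cannot move up, so they dropped the stratum condition for her. They kept the percentage. A percentage of the woman's own baseline grows with that baseline while the room left on a bounded scale shrinks, so the rule becomes harder to meet as baseline severity rises and eventually cannot be met at all.

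At stake is the only numeric change rule that staff are trained to apply to these two scales. For the highest scorers it gives no signal on the affected scale at weeks 16, 20 or 24, and review then rests on the plan's non-numeric routes. Section 2.1 intends to recruit across the full range of symptom severity, so women with high baselines are part of the target population.

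**Working it through.** **Inputs.** The threshold is a follow-up score above 1.5 times baseline (8.3.4). The maxima are M = 60 for the STAI (9.4.2) and M = 56 (8.2) or M = 14 (9.4.2) for the SHAPS. The plan states no figure of its own to reproduce.

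**Formula.** From baseline b the rule can fire only if M > 1.5 × b, that is, b < 2M/3. Taking whole-number scores:

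| Scale and range | 2M/3 | First blocked baseline | Largest possible rise there | Largest rise one point lower | Blocked score values |
|---|---|---|---|---|---|
| STAI 0-60 | 40.0 | 40 | 20/40 = 50.0% | 21/39 = 53.8% | 40-60: 21 of 61 |
| SHAPS 14-56 | 37.3 | 38 | 18/38 = 47.4% | 19/37 = 51.4% | 38-56: 19 of 43 |
| SHAPS 0-14 | 9.3 | 10 | 4/10 = 40.0% | 5/9 = 55.6% | 10-14: 5 of 15 |

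On STAI 0-60, a woman going from 40 to the maximum rises by exactly 50%, which is not above 50%, and is not flagged. The largest unflagged rises from the first blocked baseline are 20, 18 and 4 points. The last column counts possible scores, not women.

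**Other readings of the rule.**
- At least 50% instead of more than 50%: only the STAI 0-60 start moves, from 40 to 41.
- Percentage measured above the scale floor, which the plan does not describe: SHAPS 14-56 is blocked from 42; the two ranges that start at 0 are unchanged.
- STAI scored 20-80, an assumption: blocked from 54 (1.5 × 54 = 81 > 80), 27 of 61 score values.

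A blocked zone remains in every case.

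**Relation to the STAI level of 40.** Section 8.2 does not say which item coding that level uses. If it is on 0-60, all 21 scores at or above it are blocked. If it belongs to a 1-4 item coding (assumed), 20 items shift it to 40 − 20 = 20 on 0-60. Scores 20-39 can then still trigger, and 21 of the 41 scores from 20 to 60 cannot. On either coding, any STAI rise from a blocked baseline ends above the level that 8.2 calls clinically significant.

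**Effect of a point trigger.** With a trigger of D points, the unreachable baselines are those with b + D > M, which is D score values:
- STAI 0-60: 10 of 61 for D = 10; 5 of 61 for D = 5.
- SHAPS 14-56: 5 of 43 for D = 5.
- SHAPS 0-14: 2 of 15 for D = 2.

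Review of any score at the maximum covers those that remain.

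**The case against.** The strongest reply is that the plan does not rely on this sentence alone. Section 8.3.3.1 grades an increase in anxiety or anhedonia at clinically meaningful levels as a moderate adverse event, with no percentage, and 8.3.4 says "Moderate AEs will prompt a follow-up evaluation of the subject within one week". Since every STAI rise from a blocked baseline ends above the level of 40, that wording plausibly catches most of them. Other routes need no percentage either:
- section 8.3.4: the unquantified provision on symptom elevations, reports of bothersome side effects, mood deterioration reported by telephone, and clinician suicide assessment at the sessions where both scales are given;
- section 7.2: the psychologist's judgment on mood deterioration;
- section 8.3.5: monthly review of study data;
- section 10.1.6: six-monthly DSMB review of recorded symptoms.

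The other scale may also trigger. The rule requires review above 50% but does not forbid it below. And section 5.2 excludes users of psychotropics, so very high baselines may be uncommon.

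Most of this stands, and it limits the weight of the point. It does not make the sentence work. None of these routes is a numeric rule on the scores. The coordinator's duty in 8.3.4 to report significant deterioration refers the reader forward, most naturally to the same 50% rule, and the provision on elevations can also be read as referring back to it. Section 8.3.3.1 gives no SHAPS level and does not say how staff apply its wording to scale scores, least of all for a woman already at a clinically meaningful level. Cover is therefore reasonable for the STAI and less clear for the SHAPS.

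**Conclusion.** The point holds as a minor safety gap. On every range the documents state, the high-stratum rule cannot fire on a scale from about two-thirds of its maximum upward: STAI 40, SHAPS 38 or SHAPS 10. This is exact and rests only on the stated ranges and on reading the percentage as relative to the woman's own baseline, as 8.3.4 words it.

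A reader might infer more, and the documents do not support it:
- *That worsening in these women goes unmonitored.* The routes listed above remain.
- *That no high-stratum woman can trigger the rule.* Those below two-thirds of the maximum still can.
- *That about a third of women are affected* (21/61 = 34%). The counts are of score values. Without stratum cut-points or a baseline distribution, the share of women is unknown.
- *That endpoints, power or the adverse event comparison between arms are compromised.* Nothing here shows that.

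**What to change.** Leave both existing >50% sentences in 8.3.4 unchanged for women not in a high stratum, including the one with no stratum condition. Dropping that one would narrow monitoring of low and medium scorers.

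Add a rule for any woman who, on a given scale, is in a high stratum at baseline or has a baseline at or above about two-thirds of the maximum (STAI 40; SHAPS 38 or 10, according to the range used). A clinician reviews any rise from baseline on that scale of at least a small fixed number of points, and any post-baseline rise to, or score at, the maximum. The study clinicians set the number; 5 STAI points is only an illustration, and the documents supply no value. The baseline criterion is needed because the stratum cut-points are not stated. State that such a rise is assessed under the moderate adverse event wording of 8.3.3.1, so that no parallel pathway is created. The SHAPS start value cannot be written until one of the two SHAPS ranges is chosen.

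The cost is one or two sentences, the matching staff training text and some additional case reviews. No new assessments are needed, since both scales are already given at weeks 8, 16, 20 and 24. The threshold should not be set as low as any increase without accepting many reviews. With four exchangeable scores and no ties, a stable woman would exceed her baseline at least once with probability 1 − 1/4 = 3/4. That is an upper figure; it is lower in women selected for a high baseline, and a fixed point threshold reduces it further.
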